6.2.4 Monitoring and Criteria for Withholding Study Drug

6.2.4.1 Renal Monitoring and Criteria for Withholding Study Drug

Prior to each dose, the Investigator should review the following:

- Urine dipstick sample results from that day.
- Serum cystatin C results collected predose at the previous visit.
- Quantitative urinalysis collected predose at the previous visit.
- If serum cystatin C or quantitative urinalysis results are available from an unscheduled laboratory sample collected between the weekly visits, those results should be reviewed instead.

Dosing Decisions Based on Urine Testing Parameters

- **All 3 Tests Normal:** if the local dosing-day dipstick is normal, and the previous visit serum cystatin C and quantitative urinalysis are normal, dosing may occur on that day.

Local Dipstick Abnormal:

- If the result (protein, RBC, WBC) is abnormal (1+ or greater) and remains so after hydration and repeat testing, dosing should be held, and a local quantitative urinalysis should be performed. If this result is normal, dosing can proceed.

Local Quantitative Abnormal:

- If local quantitative results are abnormal (protein, RBC, WBC) (protein/osmolality ratio of >0.2 mg/mOsm; RBC or WBC abnormal per local reference ranges), and remains so after hydration and repeat testing, the dose should be held, and the results should be confirmed at the central laboratory. In addition, a 24-hour quantitative urine collection should be obtained, and if this result is normal and the urine dipstick is normal, then dosing can resume at the next scheduled visit day.

Quantitative Urinalysis (central laboratory) and Serum Cystatin C

If quantitative urinalysis is abnormal, and serum cystatin C is within the normal range but elevated by $\geq 50\%$ and $<100\%$ from baseline, dosing should be held until weekly urinalysis (central) is normal and serum cystatin C returns to a level of $<50\%$ elevation from baseline. Dosing can resume at the next scheduled visit day.

If serum cystatin C is within the normal range but elevated by $\geq 50\%$ and $<100\%$ from baseline, and urine protein is normal (according to central quantitative urinalysis and local dipstick) without an increase in RBCs or WBCs, dosing should be held until serum cystatin C returns to a level that represents $<50\%$ elevation from baseline. Dosing can resume at the next scheduled visit day.

- **If quantitative urinalysis (central laboratory) is abnormal, but serum cystatin C is unchanged compared to baseline** and in the normal range, dosing should be held until weekly central urinalysis is normal (and weekly serum cystatin C remains unchanged and in the normal range). Dosing can then resume at the next scheduled visit day.
- **If serum cystatin C is above the normal range and elevated by $>50\%$ and $<100\%$ from baseline, dosing should be held.** The following steps will be taken, depending on the quantitative urinalysis assessment:
 - **If quantitative urinalysis (central laboratory) is normal** (normal protein without an increase in RBCs or WBCs), serum cystatin C assessments will be assessed weekly until values are $<50\%$ elevation from baseline and within the normal range. Dosing can resume at the next scheduled visit day.
 - **If quantitative urinalysis (central) is abnormal**, weekly urine assessments will be performed until values return to normal. In addition, serum cystatin C assessments will be performed weekly until values are $<50\%$ elevation from baseline and within the normal range. Dosing can resume at the next scheduled visit day.
- **If serum cystatin C is elevated by $>100\%$ from baseline**, study drug will be held and a 24-hour urine collection and assessment will be performed.
 - **If the 24-hour urine assessment, including protein, albumin, WBC and RBCs, is normal**, study drug will be held and weekly serum cystatin C assessments will be performed until values are $<50\%$ elevation from baseline and within the normal range. Dosing can resume at the next scheduled visit day.
 - **If the 24-hour urine assessment, including protein, albumin, WBC and RBCs, is abnormal**, study drug will be discontinued and weekly 24-hour urine collections will be repeated until normal. In addition, weekly serum cystatin C assessments will be performed until values are $<50\%$ elevation from baseline and within the normal range. Weekly 24-hour urine collections and serum cystatin C monitoring can be

discontinued at the Investigator's discretion, even if not all values have returned to normal, when at least 2 consecutive assessments have shown stable values; however, the patient should be followed until resolution of abnormal values (according to the local guidelines).

- **If urine protein/osmolality ratio is >0.2 mg/mOsm, then the dose should be held and 24-hour urine monitoring performed weekly until it returns to the normal range. Dosing can then resume at the next scheduled visit day, provided serum cystatin C is at <50% elevation from baseline and in the reference range (other urine parameters and serum cystatin C need to be normal to resume study drug administration).**

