2.2 Rationale for the Doses and the Dosing Regimen

Two doses, 3 and 4.5 mg/kg were selected based on in vitro and in vivo pre-clinical studies, tolerability profiles in Phase 1, and the safety margin provided by toxicity studies. Based on in vitro and in vivo nonclinical studies, target engagement is expected at both 3 and 4.5 mg/kg in DMD patients. The extrapolation was based on patient plasma concentrations, muscle to plasma ratios in monkeys, differences between healthy and diseased muscle³⁷, and the measured exon skipping in monkeys. The muscle concentrations in DMD patients were predicted to be approximately 0.05 to 0.43 µg/g at 4.5 mg/kg following single-dose. However, it has been demonstrated that oligonucleotides have 4- to 10-fold higher distribution in DMD muscles as compared to normal muscles³⁷. This potential for increased penetration, due to greater permeability of the cell membrane as compared to healthy cynomolgus monkeys with intact muscle tissue integrity, should result in greater target engagement in DMD patients. Therefore, by applying these correction factors, it is anticipated that WVE-210201 concentrations following repeat administration of 4.5 mg/kg would be approximately 0.19 to 1.73 µg/g (4-fold) or 0.47 to 4.31 µg/g (10-fold). Similarly, the concentration at 3 mg/kg would be estimated at 0.13 to 1.2 µg/g (4-fold) or 0.31 to 2.9 µg/g (10-fold). The projected muscle concentrations in DMD patients at 3 and 4.5 mg/kg are similar to or above the ranges at which exon skipping was observed in the monkey and suggest that doses of 3 mg/kg and 4.5 mg/kg in patients with DMD would be predicted to lead to the tissue concentrations needed to engage the target. Due to the semi-quantitative nature of exon skipping measurement, the translation of target engagement to dystrophin protein restoration and to clinical efficacy is to be determined.

Based on Phase 1 tolerability profiles, both 3 and 4.5 mg/kg dose levels are anticipated to be generally well tolerated.

Findings in toxicology studies as well as in the human experience to date are readily monitorable in patients. This study includes weekly renal and hepatic monitoring. Specifically, weekly renal monitoring includes proteinuria, urine RBC and WBC, and serum cystatin C. If urine protein is >0.2 g/L then the dose should be held and 24-hour urine monitoring performed weekly until it returns to the normal range. Evaluation of coagulation parameters is also performed regularly.

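### Section 6.2.4.1: cystatin C above range with a rise of 50% or less triggers no cystatin C hold, and the dipstick branch can then release dosing with no cystatin C condition

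*Combined protocol and SAP*

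**What the plan says.** Before each infusion the Investigator reviews that day's dipstick and the previous visit's serum cystatin C and quantitative urinalysis (Section 6.2.4.1). The relevant rules in that section are these.

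- **All 3 Tests Normal.** If the dipstick is normal and "the previous visit serum cystatin C and quantitative urinalysis are normal, dosing may occur on that day".
- **Dipstick branch.** If the dipstick stays abnormal after hydration and a repeat, dosing is held and "a local quantitative urinalysis should be performed. If this result is normal, dosing can proceed".
- **Local quantitative branch.** If the local result stays abnormal for protein, RBC or WBC, the dose is held and a 24-hour urine is collected; "if this result is normal and the urine dipstick is normal, then dosing can resume at the next scheduled visit day".
- **Central urinalysis abnormal.** There is a hold when central urinalysis "is abnormal, but serum cystatin C is unchanged compared to baseline" and in range, and another when cystatin C is in range but up by 50% to under 100%.
- **Cystatin C above range.** The hold begins "If serum cystatin C is above the normal range and elevated by" and then gives limits of more than 50% and less than 100% over baseline.
- **Large rise.** A rise of more than 100% is held whatever the range.
- **Restart.** After these last two holds, where restart is allowed, values must show less than 50% "elevation from baseline and within the normal range. Dosing can resume at the next scheduled visit day". After a hold for a urine protein/osmolality ratio above 0.2 mg/mOsm, dosing resumes "provided serum cystatin C is at <50% elevation from baseline and in the reference range".

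Section 2.2 adds that "weekly renal monitoring includes proteinuria, urine RBC and WBC, and serum cystatin C".

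**The concern.** The above-range hold needs two things at once: a value outside the range and a rise of more than 50%. A boy whose baseline is already fairly high can leave the normal range on a smaller rise, and no cystatin C rule then tells the site to hold. For a boy already on hold, the section treats the same value as too high to resume.

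This would matter little if every route to dosing required a normal cystatin C, but the dipstick branch does not. For the same cystatin C, a boy with an abnormal dipstick can reach a sentence that releases the dose, while a boy with a normal dipstick cannot.

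Section 1.3 reports kidney findings in mice and monkeys and gives possible nephrotoxicity as the reason for monitoring kidney function. These rules are the check before each weekly infusion in children. What is at stake is patient safety and consistency between sites.

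**Working it through.** The plan states no figure to reproduce, so the check applies the rules as written. All inputs come from Section 6.2.4.1.

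**Step 1. Which cystatin C hold reaches an above-range value with a rise of 50% or less?**

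- In-range holds (rise of at least 50% and under 100%): no, because they require an in-range value.
- Abnormal central urinalysis with cystatin C unchanged: no, because it also requires an in-range value.
- Above-range hold: no, because it requires a rise of more than 50%.
- Large-rise hold: no, because it requires a rise of more than 100%.

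Rises of 0, 20, 49 and 50% were run with central urinalysis normal and with it abnormal: 4 x 2 = 8 cells. None meets a cystatin C or central urinalysis hold. A protein/osmolality ratio above 0.2 mg/mOsm has its own hold and is set aside here.

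**Step 2. Would the restart rules accept the value?** Four require both a rise under 50% and an in-range value: above range with normal urinalysis; above range with abnormal urinalysis; a rise above 100% with a normal 24-hour urine; and the protein hold. An above-range value fails all four in all 8 cells.

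**Step 3. Where does each local-urine path lead?** (Cystatin C above range, rise 50% or less, protein/osmolality not above 0.2 mg/mOsm.)

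| Local urine | What the text gives |
|---|---|
| Dipstick normal | Fails All 3 Tests Normal; dosing not cleared |
| Dipstick persistently abnormal, local quantitative normal | Dosing released; no cystatin C condition |
| Local RBC/WBC abnormal, then 24-hour urine and dipstick normal | Dosing may resume at the next visit; no cystatin C condition in the sentence, but the pre-dose review applies again |

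**Step 4. Central RBC/WBC abnormality.** With cystatin C unchanged and in range, it is held. With cystatin C above range and up 50% or less, no central rule covers it. The worse renal picture has the weaker written rule.

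**Step 5. Width of the gap.** The documents give no cystatin C reference range, so values are in assumed multiples of the ULN. The gap is ULN < value <= 1.5 x baseline, which requires baseline > 1/1.5 = 0.67.

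| Baseline (x ULN) | Upper end = 1.5 x baseline | Gap (x ULN) |
|---|---|---|
| 0.70 | 1.05 | 1.00 to 1.05 |
| 0.80 | 1.20 | 1.00 to 1.20 |
| 0.90 | 1.35 | 1.00 to 1.35 |
| 1.00 | 1.50 | 1.00 to 1.50 |

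Example at baseline 0.90: a value of 1.30 is a rise of 1.30/0.90 - 1 = 44.4%, so there is no cystatin C hold. A boy with the same baseline held at 1.40 (1.40/0.90 - 1 = 55.6%) could not restart at 1.30. By contrast, a boy going from 0.60 to 0.90 (0.90/0.60 - 1 = 50.0%, still in range) is held.

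**Step 6. Minor edges.** A rise of exactly 100% falls between the bands; in range with normal urine, it passes All 3 Tests Normal. Taken literally, the word for no change in the abnormal-urinalysis rule leaves an in-range rise of 1 to 49% with a central RBC/WBC abnormality unassigned, although local RBC/WBC holds would still apply.

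**The case against.** The best reply is that each local-urine branch lifts only the urine hold that it imposed, and the rest of the pre-dose review still governs. Cystatin C is on the review list, the notes to Table 1 send sites back to these criteria before dosing, and a parenthesis in the protein rule shows that the sponsor expects cystatin C to be normal before resumption. If a release sentence overrode everything, it would also clear a boy at +150%, against the explicit hold.

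Part of this stands. An Investigator could well infer a hold, and the explicit cystatin C holds do apply on top of the branches. But no explicit hold exists for this value. Nor can All 3 Tests Normal fill the space: it can never be met with an abnormal dipstick, so the dipstick branch has to be a separate permission. The parenthesis sits inside a rule triggered by protein above 0.2 mg/mOsm and does not reach the other cases.

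Two stronger readings are tempting, and the documents support neither.

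- A reader might infer that a restart test stricter than the hold test is itself an error. It is not: in Section 6.2.4.2 platelets are held below 100,000/µL with symptoms and restart above 150,000/µL. The 1.30 versus 1.40 contrast alone would be ordinary hysteresis.
- A reader might infer that both local branches clear the boy equally. The local quantitative branch only allows resumption at the next scheduled visit, where cystatin C is reviewed again.

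Other safeguards remain: weekly retesting, the renal insufficiency exclusion, Investigator discretion to stop treatment, and unblinded safety review by the data monitoring committee.

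**Conclusion.** The concern holds on the wording of Section 6.2.4.1, within limits. An above-range cystatin C with a rise of 50% or less has no stated cystatin C hold, and one path, the abnormal dipstick followed by a normal local quantitative urinalysis, leads to text that releases dosing at a value the section treats as too high to resume. The local RBC/WBC branch lacks the same condition but matters less. The uncovered central RBC/WBC case is a further gap; the edges in Step 6 are minor.

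The size is known only as a window, from the ULN to 1.5 times baseline for baselines above 0.67 x ULN, in assumed multiples. Frequency cannot be estimated from the documents. No efficacy endpoint or analysis is affected. Confidence is medium, because a site could reasonably infer the missing hold. The change should be made, since a dosing rule in a paediatric trial should not depend on that inference.

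**What to change.** In Section 6.2.4.1:

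1. Make the above-range hold apply to any serum cystatin C above the normal range, whatever the rise and whatever the local urine result, with weekly repeat and the existing restart test. This also covers the central RBC/WBC case.
2. Add to the release sentences of the dipstick and local quantitative branches the proviso that cystatin C is in range and less than 50% above baseline.
3. As tidying only, use at least 50% to under 100%, and at least 100%, as the limits throughout, and replace the undefined reference to no change with a rise of less than 50%.

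With these changes a cystatin C hold applies when the value is above range or the rise is at least 50%. That is the exact complement of the restart test (in range and under 50%).

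The cost is an amendment to one section and to any site dosing checklist, with no added test or visit. A few more doses may be held, mainly in boys whose baseline is near or above the ULN and whose values fluctuate across it. All 3 Tests Normal already does not clear those boys when they are above range.

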6.2.4.2 Monitoring for Thrombocytopenia and Criteria for Withholding Study Drug

Patients will be closely monitored for thrombocytopenia. Prior to each dose, samples for assessments of platelets will be collected and analyzed locally. Abnormal results should be repeated locally for confirmation. Concurrent samples should also be collected and sent to the central laboratory for analysis. Local results should be reviewed against the following criteria:

- If platelet values fall to <100,000 platelets/ μ L and the patient has new clinical signs or symptoms indicative of thrombocytopenia, drug will be held. Dosing can resume when symptoms have resolved and platelets are >150,000 platelets/ μ L.
- If platelet values fall to <50,000 platelets/ μ L, drug administration will be discontinued and the patient will be followed until resolution.
- If a platelet measurement is uninterpretable, a repeat platelet count should be obtained as soon as possible using a sodium citrate tube.
- **Note:** For patients who experience a decrease in platelets to <75,000 platelets/ μ L, an antiplatelet antibody test should be performed. If the result is indeterminate, the test should be repeated. In the case that the anti-platelet antibody test is positive, a repeat test should be performed at end of treatment.

6.3 Management of Clinical Supplies

6.3.1 Study Drug Packaging and Storage

WVE-210201 or placebo solution for infusion is supplied in a single-use 10 mL Type 1 clear glass vial with a Teflon lined rubber stopper, aluminum overseal, and plastic flip-off cap. Each vial contains 20 mg/mL WVE-210201 or placebo. Study drug will be stored at -20°C in a locked area accessible only to the pharmacy personnel. The diluted infusion solution should be stored in accordance with instructions in the Pharmacy Manual.

All study drug will be transported, received, stored, and handled in accordance with the container or product label, the instructions supplied to the pharmacy, the relevant institution's Standard Operating Procedures (SOPs), and applicable regulations. Appropriate storage and transportation

conditions will be maintained for the study drug from the point of manufacture up to delivery of the study drug.

Partially used, unused, or damaged study drug vials should be returned to the Sponsor per instructions included in study-specific manuals.

6.3.2 *Investigational Drug Accountability*

The Investigator will maintain accurate records of receipt of drug supplies, including dates of receipt. In addition, accurate records will be kept regarding when each treatment is administered, which patients received treatment, and the name of the personnel administering the treatment. Reasons for departure from the expected treatment regimen must also be recorded. Only trained site staff are permitted to treat study patients. A study monitor will review the accountability records onsite.

6.3.3 *Other Supplies*

Study sites will be provided with the Investigator's Brochure (IB), study-specific manuals, laboratory kits, and other materials, as appropriate.

7 BLINDING PROCEDURES

7.1 Blinding

This is a randomized, double-blinded, placebo-controlled study with an OL treatment period. During the double-blind period, ALL study personnel will also be blinded to patient treatment assignment (WVE-210201 or placebo). All study personnel will be blinded to assigned dose level for a given patient (i.e. 3 or 4.5 mg/kg WVE-210201 or placebo), with the exception of the pharmacist who will need to prepare study drug (WVE-210201 or matched placebo) for infusion based on dose level and patient weight. However, the pharmacists WILL be blinded as to whether a given patient receives WVE-210201 or placebo. The patient's treatment assignment in this double-blinded period will remain blinded until the end of the study (EOS).

During the OL period, all patients will receive WVE-210201, however, all study personnel will remain blinded to patient's prior treatment assignment until the EOS. Study personnel will also remain blinded to the patient's dose level (i.e., 3 or 4.5 mg/kg WVE-210201) during the OL period, with the exception of the pharmacist who will need to prepare study drug for infusion based on dose level and patient weight.

Physicians, nurses, patients, and any study personnel performing patient assessments must NOT be informed of the patient's treatment assignment except in the event of a medical emergency or as required by regulatory authorities ([Section 7.2](#)). To protect the integrity of the blind functional assessments must be completed by an assessor who has not been involved in administration of the study drug or assessment and recording of AEs at any point during the study. The same assessor should perform the assessments throughout the study for a given patient to minimize variability of assessments.

7.2 Breaking the Blind

7.2.1 *Unblinding for Medical Emergency:*

A patient's treatment assignment should remain blinded until the end of the study. However, in the event of a medical emergency, when the medical treatment of the patient depends on knowing the study treatment the patient received, the treatment blind may be broken through the IXRS system. The Investigator must document the reasons for unblinding in the patient's source documents. *The Investigator is strongly advised not to divulge the patient's treatment assignment to any individual not directly involved in managing the medical emergency nor to personnel involved with the analysis and conduct of the study.*

7.3 Recording the Unblinding

If an unblinding occurs, the date on which the code was broken, together with the identity of the person responsible for breaking the blind, must be documented in the patient's source documents. The unblinded treatment information will not be disclosed to the Sponsor. In consultation with the Medical Monitor and the Sponsor, the patient may be withdrawn from the study if the blind is broken.

The documentation should include, but is not limited to, the following information:

- Patient information
- Reason for unblinding
- Date and time of unblinding
- Name of the person requesting/responsible for unblinding

8 METHODS OF ASSESSMENT AND ENDPOINTS

8.1 Safety Assessments

The safety assessments will include the following:

- Adverse events (Section 9)
- Medical history and demographics
- Prior and concomitant medications
- Physical examinations (including neurological and psychiatric)
- Vital signs

- Height and weight
- 12-lead ECGs
- Clinical laboratory evaluations (including clinical chemistry, hematology, and urinalysis)
- Echocardiogram

Any abnormal laboratory test results (hematology, clinical chemistry, or urine) or other safety assessments (e.g., vital sign measurements), that are assessed as clinically significant in the medical and scientific judgment of the Investigator are to be recorded as AEs or SAEs.

8.1.1 *Medical History and Demographics*

A general medical history will be obtained at the Screening visit. Investigator assessment of past medical history at Screening will include information regarding any significant medical, surgical, psychiatric, and/or neurological conditions and treatments.

8.1.2 *Prior and Concomitant Medications*

Medications with a start date before the first dose of investigational drug will be classified as prior medications. Any medication that the patient began taking after the first dose of investigational drug will be classified as concomitant. Any medication that a patient started before the first dose of investigational drug and continued to take during the study will be classified as both prior and concomitant. Any medication that was stopped on the same day (prior to dosing) as the first dose of investigational drug will be considered a prior medication. If the stop date of a given medication is missing, then the medication will be classified as concomitant.

Any history of steroid and/or investigational drug use will be captured. Prior treatments for DMD (e.g., approved ASO) given at any time in the patient's history should be captured.

The minimum requirement is that the drug name, dose, indication, and the dates of administration are to be recorded. This will include all prescription drugs, herbal products, vitamins, minerals, and over-the-counter medications. Any changes in concomitant medications will also be recorded in the patient's eCRF.

Any concomitant medication deemed necessary for the welfare of the patient during the study may be given at the discretion of the Investigator. It is the responsibility of the Investigator to ensure that details regarding the medication are recorded in full in the eCRF.

8.1.3 *Physical Examination*

A complete physical examination will be performed at the time points noted in the Schedule of Assessments ([Table 1](#) and [Table 2](#)). At Screening, Weeks 48 and 96, the physical examination will include (but is not limited to) an examination of skin, head, eyes, ears, nose, throat,

respiratory, cardiovascular, gastrointestinal, endocrine, metabolic, blood, lymphatic, musculoskeletal, psychiatric, and neurologic (including mental status, cranial nerves, motor system, reflexes, coordination and gait, and sensory system) systems.

At all other time points (approximately every 4 weeks), the physical examination must include (at a minimum) head, eyes, ears, nose, throat, respiratory, cardiovascular, gastrointestinal, musculoskeletal, psychiatric, and neurologic). Other systems should be evaluated as appropriate.

Physical findings will be recorded in the eCRF and source documents.

8.1.4 *Vital Signs (Blood Pressure, Heart Rate and Temperature)*

Vital sign measurements will be taken as per standard site practice, after the patient has been resting quietly (either lying flat or sitting, whichever is most appropriate for the condition of the patient) for a period of at least 5 minutes. Blood pressure (systolic and diastolic), temperature, and pulse will be measured by medically qualified personnel at the time points described in the Schedule of Assessments ([Table 1](#) and [Table 2](#)) and recorded in the eCRF and source documents. As feasible, the same position (either sitting or lying) should be used for all subsequent blood pressure measurements during the study for an individual patient. If the initial reading is high, the measurements will be repeated twice and the average of the three readings will be used.

8.1.5 *Height and Weight*

The patient's height and weight will be measured at the time points described in the Schedule of Assessments ([Table 1](#) and [Table 2](#)) and recorded in the eCRF and source documents.

8.1.6 *12-Lead ECG*

Computerized, good quality, 12-lead ECGs will be collected in triplicate and recorded at the time points described in the Schedule of Assessments ([Table 1](#) and [Table 2](#)). Recordings will be obtained in the supine position after the patient has rested comfortably for ≥ 5 minutes.

The ECG tracing will be submitted and read by a centralized reviewer (details will be provided in a study-specific manual). The following should be recorded on the trace and eCRF: whether the ECG is normal or abnormal and, if deemed abnormal, whether the abnormality is clinically significant or not clinically significant, including a note of the abnormality.

8.1.7 *Echocardiogram*

A standard 2-dimensional (2D) ECHO will be obtained at the time points specified in [Table 1](#) and [Table 2](#), and the results recorded in the eCRF and source documents.

ECHOs should be performed at a consistent time of day throughout the study. The Investigator will review the results of the ECHO report and determine if the findings are clinically significant. Results will be submitted and read by a centralized reviewer (details will be provided in a study-specific manual).

